Appendix 1. Programming Conventions for Outputs

Dates & Times

Depending on data available, dates and times will take the form yyyy-mm-ddThh:mm:ss.

Presentation of Arm

For outputs, group will be represented as follows and in that order:

Group	For Tables, Listings and Graphs
Arm 1	Arm 1
Arm 2	Arm 2

Presentation of Visits

For outputs, visits will be represented as follows and in that order:

Long Name (default)	Short Name
Screening (Visit 1)	Scr (V1)
Baseline (Visit 2)	BL (V2)
Week 3 (Visit 3)	W3 (V3)
Week 7 (Visit 4)	W7(V4)
---	---
Week 23 (Visit 8)	W23 (V8)
Week 27 (Visit 9)	W27 (V9/EOS)
Early Discontinuation Visit	EDV
Week 31 (Visit 10)	W31 (V10)

Listing Order

All listings will be ordered by the following (unless otherwise indicated in the template):

- Center-subject ID,
- Date (where applicable)

Appendix 2. Partial Date Conventions

Imputed dates will NOT be presented in the listings.

Algorithm for Adverse Events:

START DATE	STOP DATE	ACTION
Known	Known	If start date < study med start date, then not AE If start date \geq study med start date, then AE
	Partial	If start date < study med start date, then not AE If start date \geq study med start date, then AE
	Missing	If start date < study med start date, then not AE If start date \geq study med start date, then AE
Partial, but known components show that it cannot be on or after study med start date	Known	Pre-treatment events
	Partial	Pre-treatment events
	Missing	Pre-treatment events
Partial, could be on or after study med start date	Known	If stop date < study med start date, then Pre-treatment events If stop date \geq study med start date, then AE
	Partial	Impute stop date as latest possible date (i.e. last day of month if day unknown or 31st December if day and month are unknown), then: If stop date < study med start date, then Pre-treatment events If stop date \geq study med start date, then AE
	Missing	Assumed AE
Partial, and known components show that it	Known	AE
	Partial	AE
	Missing	AE

START DATE	STOP DATE	ACTION
is on or after 361-201 study med start date		
Missing	Known	If stop date < study med start date, then Pre-treatment events If stop date \geq study med start date, then AE
	Partial	Impute stop date as latest possible date (i.e. last day of month if day unknown or 31st December if day and month are unknown), then: If stop date < study med start date, then not AE If stop date \geq study med start date, then AE
	Missing	Assumed AE

Algorithm for Prior / Concomitant Medications:

START DATE	STOP DATE	ACTION
Known	Known	If stop date < study med start date, assign as prior If stop date >= study med start date and start date <= end of treatment, assign as concomitant If stop date >= study med start date and start date > end of treatment, assign as post treatment
	Partial	Impute stop date as latest possible date: 
 • If only day unknown, impute as the earlier of (last day of month, end date of the last study visit) • If month and day unknown, impute as the earlier of (31st December, end date of the last study visit). Then: If stop date < study med start date, assign as prior If stop date >= study med start date and start date <= end of treatment, assign as concomitant If stop date >= study med start date and start date > end of treatment, assign as post treatment
	Missing	If stop date is missing could never be assumed a prior medication If start date <= end of treatment, assign as concomitant If start date > end of treatment, assign as post treatment

START DATE	STOP DATE	ACTION
Partial	Known	
Impute start date as earliest possible date: Source questions: 'started prior to start of study?' = Yes; 'Started after last dose of study medication?' = No.
 
 • If only day unknown, impute as the later of (first day of the month). • If month and day unknown, impute as the later of (1st January). 
Source questions: 'Started prior to study?' = No; 'Started after last dose of study medication?' = Yes.
 
 • If only day unknown, impute as the later of (first day of the month; end of treatment + 1). • If month and day unknown, impute as the later of (1st January; end of treatment + 1). 
Source questions: 'Started prior to study?' = No; 'Started after last dose of study medication?' = No.
 
 • If only day unknown, impute as the later of (first day of the month; date of ICF). • If month and day unknown, impute as the later of (1st January; date of ICF). 
Then:
 
If stop date < study med start date, assign as prior.
 
If stop date \geq study med start date and start date \leq end of treatment, assign as concomitant.
 
If stop date \geq study med start date and start date $>$ end of treatment, assign as post treatment.

		
treatment, assign as concomitant.
 
If stop date \geq study med start date and start date $>$ end of treatment, assign as post treatment.

	Partial	

START DATE	STOP DATE	ACTION
		
Impute start date as earliest possible date: Source questions: 'Started prior to study?' = Yes; 'Started after last dose of study medication?' = No.
 
 • If only day unknown, impute as the later of (first day of the month; date of birth). • If month and day unknown, impute as the later of (1st January). 
Source questions: 'Started prior to study?' = No; 'Started after last dose of study medication?' = Yes.
 
 • If only day unknown, impute as the later of (first day of the month; end of treatment + 1). • If month and day unknown, impute as the later of (1st January; end of treatment + 1). 
Source questions: 'Started prior to study?' = No; 'Started after last dose of study medication?' = No.
 
 • If only day unknown, impute as the later of (first day of the month; date of ICF). • If month and day unknown, impute as the later of (1st January; date of ICF). 
Impute stop date as latest possible date:
 
 • If only day unknown, impute as the earlier of (last day of the month; end date of the last study visit). 
assign as prior. If stop date \geq study med start date and start date \leq end of treatment, assign as concomitant. If stop date \geq study med start date and start date $>$ end of treatment, assign as post treatment.

START DATE	STOP DATE	ACTION
		
 • If month and day unknown, impute as the earlier of (31st December; end date of the last study visit). 
Then:
 
If stop date < study med start date, assign as prior. If stop date \geq study med start date and start date \leq end of treatment, assign as concomitant. If stop date \geq study med start date and start date $>$ end of treatment, assign as post treatment.

Missing		
Impute start date as earliest possible date:
 
Source questions: 'Started prior to study?' = Yes; 'Started after last dose of study medication?' = No.
 
 • If only day unknown, impute as the later of (first day of the month; date of birth). • If month and day unknown, impute as the later of (1st January). 
Source questions: 'Started prior to study?' = No; 'Started after last dose of study medication?' = Yes.
 
 • If only day unknown, impute as the later of (first day of the month; end of treatment + 1). • If month and day unknown, impute as the later of (1st January; end of treatment + 1). 
Source questions: 'Started prior to study?' = No; 'Started after last dose of study medication?' = No.
 
 • If only day unknown, impute as the later of (first day of the month; date of ICF). • If month and day unknown, impute as the later of (1st January; date of ICF). 
Then: If stop date is missing could never be assumed a prior medication. If start date \leq end of treatment, assign as concomitant. If start date $>$ end of treatment, assign as post treatment.

START DATE	STOP DATE	ACTION
Missing	Known	
If stop date < study med start date, assign as prior.
 
If stop date \geq study med start date and Source question 'Started after last dose of study medication?' = No, assign as concomitant.
 
If Source question 'Started after last dose of study medication?' = Yes, assign as post treatment.

	Partial	
Impute stop date as latest possible date:
 
 • If only day unknown, impute as the earlier of (last day of the month; end date of the last study visit). • If month and day unknown, impute as the earlier of (31st December; end date of the last study visit). 
Then: If stop date < study med start date, assign as prior.
 
If stop date \geq study med start date and CRF question 'Started after last dose of study medication?' = No, assign as concomitant.
 
If Source question 'Started after last dose of study medication?' = Yes, assign as post treatment.

	Missing	
If Source question 'Started after last dose of study medication?' = No, assign as concomitant.
 
If Source question 'Started after last dose of study medication?' = Yes, assign as post treatment.

Appendix 3. PCS Criteria for Laboratory Parameters

Category		
Parameter Name		
Gender Restriction, if any	PCS Low	PCS High
Hematology		
WBC	$\leq 2.8 \times 10^9/L$	$\geq 16 \times 10^9/L$
Neutrophils	$< 1.5 \times 10^9/L$	$> 13.5 \times 10^9/L$
Lymphocytes	N/A	$> 12.0 \times 10^9/L$
Monocytes	N/A	$> 2.5 \times 10^9/L$
Eosinophils	N/A	$> 1.6 \times 10^9/L$
Basophils	N/A	$> 1.6 \times 10^9/L$
Hemoglobin		
Female	$\leq 95 \text{ g/L}$	$\geq 175 \text{ g/L}$
Male	$\leq 115 \text{ g/L}$	$\geq 190 \text{ g/L}$
Hematocrit		
Female	$\leq 0.32(\text{fraction of 1})$	$\geq 0.54(\text{fraction of 1})$
Male	$\leq 0.37(\text{fraction of 1})$	$\geq 0.60(\text{fraction of 1})$
RBC	$\leq 3.5 \times 10^{12}/L$	$\geq 6.4 \times 10^{12}/L$
Platelet Count	$\leq 75 \times 10^9/L$	$\geq 700 \times 10^9/L$
Blood Chemistry		
Sodium	$\leq 126 \text{ mmol/L}$	$\geq 156 \text{ mmol/L}$
Potassium	$\leq 3 \text{ mmol/L}$	$\geq 6 \text{ mmol/L}$
Chloride	$\leq 90 \text{ mmol/L}$	$\geq 118 \text{ mmol/L}$
Bicarbonate	$\leq 16 \text{ mmol/L}$	$\geq 35 \text{ mmol/L}$
Calcium	$< 2.05 \text{ mmol/L}$	$\geq 3 \text{ mmol/L}$
Magnesium	$< 0.6 \text{ mmol/L}$	$> 1.15 \text{ mmol/L}$
Phosphate	0.65 mmol/L	1.65 mmol/L
AST	N/A	$\geq 3 \times \text{ULN}$
ALT	N/A	$\geq 3 \times \text{ULN}$

Category		
Parameter Name	PCS Low	PCS High
Gender Restriction, if any		
Alkaline Phosphatase	N/A	$\geq 3 \times \text{ULN}$
Creatinine	N/A	$\geq 177 \text{ umol/L}$
BUN	N/A	$\geq 10.71 \text{ mmol/L}$
Total bilirubin	N/A	$\geq 34.2 \text{ umol/L}$
Direct bilirubin	N/A	$\geq 17.1 \text{ umol/L}$
Indirect bilirubin	N/A	$\geq 34.2 \text{ umol/L}$
Total protein	$\leq 45 \text{ g/L}$	$\geq 100 \text{ g/L}$
Albumin	$\leq 25 \text{ g/L}$	N/A
Uric Acid		
Female	N/A	$\geq 506 \text{ umol/L}$
Male	N/A	$\geq 625 \text{ umol/L}$
Glucose	$\leq 2.22 \text{ mmol/L}$	$\geq 9.71 \text{ mmol/L}$
Urinalysis		
Ketones	N/A	$> 4+$
Glucose	N/A	$> 4+$
Thyroid Function		
Free T4	$< 9.65 \text{ pmol/L}$	$> 22.5 \text{ pmol/L}$
Free T3	$< 3.07 \text{ pmol/L}$	$> 6.38 \text{ pmol/L}$
TSH	0 mIU/L	$> 10 \text{ mIU/L}$

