2.4.4. Safety Endpoints

- Number and percentage of subjects with AEs.
- Number and percentage of subjects with serious adverse events (SAEs).
- Number and percentage of subjects with AEs leading to discontinuation.
- Electronic Columbia-Suicide Severity Rating Scale (eC-SSRS): Proportion (%) of events in each classification class (as completed by the subject).
- Changes from baseline in clinical laboratory parameters, including thyroid panel.
- Changes from baseline in vital signs parameters.
- Score of AED-specific AEs (by the Liverpool Adverse Event Profile [LAEP]).

2.4.5. **Exploratory Endpoints**

- Seizure data recorded by an investigational wearable watch device from Empatica.
- Seizure data recorded by an investigational electronic seizure diary from Empatica MATE application.

3. Study Design

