16.2. Laboratory Evaluations

Results from the central laboratory will be included in the reporting of this study for Hematology, Blood Chemistry, Urinalysis, Thyroid Panel, Renal Functioning, Urine Drug Screening, Serum Pregnancy and Urine Pregnancy Test. A list of laboratory assessments to be included in the outputs is included in Appendix 1 of the protocol, Section 20.

All laboratory summaries will be used on the safety population and presentations will use SI Units.

Quantitative laboratory measurements reported as "< X", will be converted to X for the purpose of quantitative summaries, but will be presented as recorded, i.e. as "< X" or "> X" in the listings. The following summaries and listings will be provided for laboratory data:

- For laboratory parameters with continuous outcomes (e.g. blood chemistry, hematology, urinalysis data, thyroid panel), descriptive statistics for the actual values and for changes from baseline will be presented by arm for each evaluation time point.
- For laboratory parameters with categorical outcomes (e.g. urinalysis data), the number and percentage of subjects with each outcome will be presented by arm at each evaluation time point.
- Overall summary of the post-baseline PCS will be presented. The number and percentage of subjects with PCS criteria will be summarized by arm . This summary will be also

presented by age group, race group, gender, baseline AEDs and number of baseline AEDs.

- Shifts from baseline by arm for each evaluation time point will be produced to show the percentage of subjects with laboratory test values below, within, and above the normal range.
- Data listing of all clinical laboratory measurements (hematology, blood chemistry, urinalysis, thyroid, and renal function) will be provided. Results outside of the reference range will be flagged.
- Listing of clinically significant out of range laboratory measurements, urine drug screen and serum pregnancy test results will be provided.
- A listing of PCS laboratory findings (e.g. blood chemistry, hematology, urinalysis data, and thyroid function) will be presented for all laboratory parameters with PCS criteria defined in Appendix 3.

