16.2.2. Laboratory Reference Ranges and Potentially Clinically Significant (PCS)

Quantitative laboratory measurements will be compared with the relevant laboratory reference ranges in SI units and categorized as:

Low: Below the lower limit of the laboratory reference range.

Normal: Within the laboratory reference range (upper and lower limit included).

High: Above the upper limit of the laboratory reference range.

Similarly, sponsor defined- PCS laboratory results will be identified using the criteria in Appendix 3.

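### The SAP's low-side flag for TSH is set at 0 mIU/L, a limit that no positive or below-assay result can meet, so the PCS outputs cannot show suppressed TSH

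*SAP*

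**What the plan says.** SAP Appendix 3 gives each laboratory parameter a PCS-low and a PCS-high entry. The TSH row is "TSH 0 mIU/L $> 10 \text{ mIU/L". Where a side is not used, the table says N/A, for example on the low side of AST, ALT and creatinine and the high side of albumin. Free T4 and free T3, the two rows above TSH, have working limits on both sides.

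SAP 16.2.2 makes the appendix the flagging rule: "sponsor defined- PCS laboratory results will be identified using the criteria in Appendix 3". Neither document gives another low limit for TSH.

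SAP 16.2 then uses the flags in two kinds of output. For the summary, "The number and percentage of subjects with PCS criteria will be summarized by arm", and it is repeated by age group, race group, gender, baseline AEDs and number of baseline AEDs. A listing of PCS findings, with thyroid function among its examples, "will be presented for all laboratory parameters with PCS criteria defined in Appendix 3".

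For results below a reporting limit, SAP 16.2 says that a value given as '< X' "will be converted to X for the purpose of quantitative summaries", while listings keep it as recorded.

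**The concern.** A PCS-low limit is meant to pick out markedly low values. A limit of 0 on a concentration cannot do that, because every measurable TSH lies above it. The entry is a number with a unit and not N/A, so a programmer would treat it as an active criterion and a reader of the tables would assume that it had been applied.

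What is at stake is a zero that looks like a finding. A count of no subjects with PCS-low TSH would be read as the absence of marked suppression, when the rule could hardly have produced any other count. The thyroid panel is the one laboratory group that the safety endpoints single out by name (SAP 2.4.4; Protocol 6.4), so readers are likely to look at this row.

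**Working it through.** The plan has no calculated figure to reproduce here. The check is whether any result that a laboratory could report would meet the low criterion.

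**Inputs**
- Low limit: 0 mIU/L (SAP Appendix 3).
- Operator: none in the text available for review. All three low-side readings were tried: '<', '<=' and '='.
- Below-limit results: '< X' is set to X in quantitative summaries (SAP 16.2).
- Reporting limit X of the TSH assay: not in either document. Assumed positive, with trial values of 0.001, 0.005, 0.01, 0.02, 0.05 and 0.1 mIU/L.

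**Test of each type of result against the limit of 0**

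| Result | '< 0' | '<= 0' | '= 0' |
|---|---|---|---|
| '< X' set to X (six trial values) | 0 of 6 flagged | 0 of 6 flagged | 0 of 6 flagged |
| '< X' set to X/2 (six trial values) | 0 of 6 | 0 of 6 | 0 of 6 |
| Numeric 0.001, 0.01, 0.1 or 0.4 mIU/L | not flagged | not flagged | not flagged |
| Numeric 0 exactly | not flagged | flagged | flagged |

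The outcome does not depend on the trial values of X: any X > 0 fails all three comparisons with 0, and so does X/2.

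**Dependence on the conversion rule.** SAP 16.2 states the conversion for quantitative summaries and does not say that it also governs PCS flags. If it does not, the result stays as '< X'. Knowing only that a value is below some positive X does not show that it is 0 or less, so the criterion is still not met.

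**Where low TSH remains visible.** SAP 16.2 also plans descriptive statistics and changes from baseline by time point, shift tables giving the "percentage of subjects with laboratory test values below, within, and above the normal range", a listing of all laboratory values with out-of-range flags, and a listing of clinically significant out-of-range results. None of these uses Appendix 3. The gap is therefore confined to the PCS summary, its subgroup versions and the PCS listing.

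**The case against.** The strongest reply is that little is lost. Every low TSH value is in the flagged listing, and with about 100 subjects (SAP 3.3) those listings can be read directly. Protocol 12.2 has clinically significant laboratory abnormalities recorded as adverse events. The PCS-high limits for free T4 and free T3 are usable. The safety endpoint is "Changes from baseline in clinical laboratory parameters, including thyroid panel", and PCS flags do not enter it. The study is descriptive throughout and performs no tests. All of this stands and sets the weight of the point, but it does not make the limit of 0 workable.

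Four stronger readings are tempting, and the documents do not support them:

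- **That the PCS-low count is zero with certainty.** A value recorded as exactly 0, for instance through rounding, would be flagged under '<=' or '='. The documents give neither the assay's reporting limit nor its format.
- **That the SAP's below-limit conversion is what disables the flag.** That rule is stated for quantitative summaries only. The point rests on the value 0 and does not need the rule.
- **That some number of subjects with suppressed TSH would be missed.** Neither document gives a rate of suppression, so no count can be attached. Such subjects would be absent from the PCS outputs but not from the other displays.
- **That the phosphate row is also wrong.** It reads "Phosphate 0.65 mmol/L 1.65 mmol/L", with no operators. Symbols may have been lost when the table was read from PDF, and the PCS Low and PCS High column headings already give the direction. This is something to confirm and not an error.

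The missing operator on the TSH row is likewise not counted as an error. If the 0 itself proves to be a reading fault, a look at the source table settles the matter.

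**Conclusion.** The point holds as a minor correction. As printed, the TSH PCS-low entry is an active limit that no positive result and no '< X' result can meet under '<', '<=' or '='. The only exception is a value recorded as exactly 0 under '<=' or '='. The PCS outputs would show essentially no low TSH whatever the true frequency.

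The effect is one side of one parameter in a descriptive safety display. The primary endpoint, the efficacy endpoints and the named laboratory safety endpoint are untouched.

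The conclusion assumes that the printed 0 matches the source table, and that the assay's reporting limit is above 0.

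**What to change.** Before database lock, change the TSH PCS-low cell in SAP Appendix 3 in one of two ways:

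- enter the attainable limit, with its operator, from the sponsor's PCS list or the central laboratory's limit; or
- enter N/A, as the table does for other unused sides, so that a structural zero is not reported as a finding.

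No value is proposed here, because the documents supply none. As a check only, compare the operators on the TSH and phosphate rows with the source table.

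The cost is one table cell and a short check. It needs no new data and no change to study conduct.
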